**Table 6-6 Management of non-infectious pneumonitis**

Worst grade pneumonitis	Suggested investigations	Management of pneumonitis	Everolimus dose adjustment
Grade 1	CT scans with lung windows.	No specific therapy is required	No dose adjustment required. Initiate appropriate monitoring.
Grade 2	CT scan with lung windows. Consider pulmonary function testing includes: spirometry, DLCO, and room air O 2 saturation at rest. Consider a bronchoscopy with biopsy and/or BAL. Monitoring at each visit until return to ≤ grade 1. Return to initial monitoring frequency if no recurrence.	Symptomatic only. Consider corticosteroids and/or other supportive therapy if symptoms are troublesome.	Rule out infection and consider interruption of everolimus until symptoms improve to Grade ≤ 1. Re-initiate everolimus at one dose level lower. Discontinue everolimus if failure to recover within ≤ 28 days.
Grade 3	CT scan with lung windows and pulmonary function testing includes: spirometry, DLCO, and room air O 2 saturation at rest. Monitoring at each visit until return to ≤ grade 1. Return to initial monitoring frequency if no recurrence. Bronchoscopy with biopsy and/or BAL is recommended.	Consider corticosteroids if infective origin is ruled out. Taper as medically indicated.	Rule out infection and interrupt everolimus until symptoms improve to Grade ≤ 1. Consider re-initiating everolimus at one dose level lower (approximately 50% lower than the dose previously administered depending on individual clinical circumstances) Discontinue everolimus if failure to recover within ≤ 28 days.
Grade 4	CT scan with lung windows and required pulmonary function testing, if possible, includes: spirometry, DLCO, and room air O 2 saturation at rest. Monitoring at each visit until return to ≤ grade 1. Return to initial monitoring frequency if no recurrence. Bronchoscopy with biopsy and/or BAL is recommended if possible.	Consider corticosteroids if infective origin is ruled out. Taper as medically indicated.	Rule out infection and discontinue everolimus.

For patients receiving both everolimus and temozolomide: if everolimus is stopped due to toxicity, patients may continue to be treated with temozolomide at the discretion of the treating investigator.

### 6.2.3 Management of specific temozolomide toxicities

Temozolomide will be administered every 4 weeks, unless the patient has not recovered from treatment-related adverse events associated with a prior course. Recovery has occurred once all of the following conditions have been met:

- ANC  $\geq 1500/\mu\text{L}$ ;
- Platelet count  $\geq 100,000/\mu\text{L}$ ;
- All drug-associated non-hematological toxicities have recovered to  $\leq$  grade 2 or to baseline levels and the investigator does not feel that any of these toxicities present any hazard to patient safety or care.

If recovery has not occurred by Day 28, the subsequent course of treatment will be delayed until these criteria have been met. The dose of temozolomide in subsequent courses will be individually titrated (see Table 6-7 below). Growth factors cannot be used to induce elevations in neutrophil count for the purposes of administration of temozolomide on the scheduled dosing or to allow treatment with temozolomide at a higher dose.

**Hematological Criteria:** If temozolomide cannot be administered on the scheduled day of dosing, the CBC will be repeated weekly for up to and including 4 weeks until the ANC is  $\geq 1500/\mu\text{L}$  and platelet count is  $\geq 100,000/\mu\text{L}$ . If these hematological criteria are met, chemotherapy may be administered according to the dose adjustments outlined in Table 6-5 below. If the ANC remains  $< 1500/\mu\text{L}$  or platelet count is  $< 100,000/\mu\text{L}$  at 4 weeks, the decision to restart must be reviewed with the study chair or their designated alternate before proceeding. No more than two dose reductions will be allowed.

The dose of temozolomide administered for subsequent cycles will be determined according to the nadir ANC and nadir platelet count of the immediately previous cycle for temozolomide (see Table 6-7).

**Table 6-7 Temozolomide Dose-Adjustment Criteria for Hematologic Toxicity**

Nadir Toxicity Level	Nadir ANC/ $\mu\text{L}$	Nadir Platelets/ $\mu\text{L}$	Temodar Modification
1	1500–1999	75–99, 999	Dose unchanged from previous
2	1000–1499	50–74, 999	Dose unchanged from previous
3	500–999	25–49, 999	Decrease dose to next lower dose level
4	<500	<25,000	Decrease dose to next lower dose level

---

Note: Dose levels (daily dose): 200 mg/m^2/day, 150 mg/m^2/day, 100 mg/m^2/day.

**Non-Hematological Criteria:** Subsequent courses will start (as long as the treatment is beneficial) after complete resolution of toxicities to grade 2 or less. A minimum 2-week rest period will be required if there is grade 3 or greater non-hematological toxicity, and dosages for the subsequent course will be one dose level below the dose that produced toxicity of grade 3 or greater, except doses will not be reduced for grade 3 nausea/emasis unless it is grade 3 despite optimal medical management.

If the patient experiences grade 3 or greater hematological or non-hematological toxicity after 2 dose reductions of temozolomide, he or she will discontinue temozolomide for the remainder of the study. Patients may continue to be treated with everolimus.

### **6.3 Concomitant medications**

Patients must be instructed not to take any medications (over-the-counter or other products) during the protocol treatment period without prior consultation with the investigator. The investigator should instruct the patient to notify the study site about any new medications he/she takes after the start of study drug. All medications (other than study drug) and significant non-drug therapies (including physical therapy and blood transfusions) taken within 14 days of starting study treatment through the 30-day safety follow up visit should be reported on the CRF. In particular, corticosteroid dosing will be recorded as use of corticosteroids may affect the appearance of T2 changes on MRI imaging. In addition, the definition of response is based on corticosteroid use (see Section 7.2.3).

#### **6.3.1 Permitted concomitant therapy**

Patients will be instructed not to take any additional medications (including over-the-counter products) during the course of the study without prior consultation with the investigator. At each visit, the study team will ask the patient about any new medications he/she is or has taken after the start of the study drug.

The following restrictions apply during the entire duration of the study:

- No other investigational therapy should be given to patients.
- No anticancer agents other than the study medication should be given to patients. If such agents are required for a patient then the patient must first be withdrawn from the study.

Oral contraceptives: preclinical and clinical data have shown everolimus to have CYP3A4 inhibitory activity rather than induction activity, so induction of metabolism of contraceptive hormones by everolimus is unlikely. Consequently, administration of everolimus should not reduce the efficacy of oral contraceptives.

**Cytochrome P450 and P-glycoprotein inhibitors/inducers/substrates**

Co-administration with strong inhibitors of CYP3A4 or PgP should be avoided; and may cause increased everolimus concentrations. For a current table of Substrates, Inhibitors and Inducers please access the following website:

<http://www.fda.gov/Drugs/DevelopmentApprovalProcess/DevelopmentResources/DrugInteractionsLabeling/ucm093664.htm>

Everolimus is metabolized by CYP3A4 in the liver and to some extent in the intestinal wall.

Therefore, the following are recommended:

- Co-administration with strong inhibitors of CYP3A4 (e.g., ketoconazole, itraconazole, ritonavir) or P-glycoprotein (PgP) inhibitor should be avoided.
- Co-administration with moderate CYP3A4 inhibitors (e.g., erythromycin, fluconazole) or PgP inhibitors should be used with caution. If a patient requires co-administration of moderate CYP3A4 inhibitors or PgP inhibitors, reduce the dose of everolimus. Additional dose reductions may be required to manage toxicities. If the inhibitor is discontinued, the everolimus dose should be returned to the dose used prior to initiation of the moderate CYP3A4/PgP inhibitor after a washout period of 2 to 3 days.
- Grapefruit or citrus juices affect P450 and PgP activity. Concomitant use should be avoided.
- Co-administration with strong inducers of CYP3A4 should be avoided. If a patient requires co-administration of strong CYP3A4 inducers (i.e., phenytoin, carbamazepine, rifampin, rifabutin, phenobarbital, St. John's wort), an increase in the dose of everolimus up to twice the currently used daily dose should be considered, 5 mg increments. Enzyme induction usually occurs within 7-10 days; therefore everolimus dose should be increased by one increment 7 days after the start of the inducer therapy. If no safety concerns are seen within the next 7 days, the dose can be increased again one additional increment up to a maximum of twice the daily dose used prior to initiation of the strong CYP3A4 inducer.
- This dose adjustment of everolimus is intended to achieve similar AUC to the range observed without inducers. However, there are no clinical data with this dose adjustment in patients receiving strong CYP3A4 inducers. If the strong inducer is discontinued the everolimus dose should be returned to the dose used prior to initiation of the strong CYP3A4/PgP inducer.

Please refer to Table 6-6 listing relevant inducers and inhibitors of CYP3A and Table 6-7 for a list of relevant substrates, inducers, and inhibitors of PgP.

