2. For more severe toxicity (grade 2 in which case patients have pain but are able to maintain adequate oral alimentation, or grade 3 in which case patients cannot maintain adequate oral alimentation), the suggested treatments are topical analgesic mouth treatments (i.e., local anesthetics such as, benzocaine, butyl aminobenzoate, tetracaine hydrochloride, menthol, or phenol) with or without topical corticosteroids, such as triamcinolone oral paste 0.1% (Kenalog in Orabase®).
3. Agents containing alcohol, hydrogen peroxide, iodine, and thyme derivatives may tend to worsen mouth ulcers. These agents should be avoided.
4. Antifungal agents should be avoided unless a fungal infection is diagnosed. In particular, systemic imidazole antifungal agents (ketoconazole, fluconazole, itraconazole, etc.) should be avoided in all patients due to their strong inhibition of everolimus metabolism, therefore leading to higher everolimus exposures. Therefore, topical antifungal agents are preferred if an infection is diagnosed.

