**Table 6-8      Clinically relevant drug interactions: inducers, and inhibitors of isoenzyme CYP3A**

Inducers
carbamazepine, glucocorticoids, modafinil, oxcarbazepine, phenobarbital, phenytoin, pioglitazone, rifabutin, rifampin, St. John's wort, troglitazone, efavirenz, nevirapine, topiramate, avasimibe, bosentan, etravirine, nafcillin, ritonavir, talviraline (not available in US market), tipranavir, amprenavir, aprepitant, armodafinil (R-modafinil), dexamethasone, nevirapine, prednisone, pleconaril (not available in US market), rufinamide
Inhibitors
Strong inhibitors: clarithromycin, conivaptan, indinavir, itraconazole, ketoconazole, lopinavir, mibefradil, nefazodone, nefinavir, ritonavir, saquinavir, telithromycin, troleandomycin, voriconazole, tipranavir, elvitegravir, Posaconazole ( Krishna et al 2009 )
Moderate inhibitors: aprepitant, atazanavir, casopitant, cimetidine, ciprofloxacin, darunavir, diltiazem, erythromycin, fluconazole, grapefruit juice (citrus parasida fruit juice), imatinib, tofisopam, verapamil, amprenavir, fosamprenavir, dronedarone

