### 6.3.2 Prohibited concomitant therapy

None.

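### The everolimus interaction rules contradict each other for fluconazole, PgP inhibitors and St. John's wort, cite the wrong tables, and allow doses above the top of the reduction ladder

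*Combined protocol and SAP*

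**What the plan says.** The rules on drugs that interact with everolimus are spread over several places in the protocol.

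- **Section 6.2.2.3** (mouth ulcers), item 4: "systemic imidazole antifungal agents (ketoconazole, fluconazole, itraconazole, etc.) should be avoided in all patients due to their strong inhibition of everolimus metabolism". If a fungal infection is diagnosed, topical agents are preferred.
- **Section 6.3.1, first bullet:** strong CYP3A4 inhibitors "or P-glycoprotein (PgP) inhibitor should be avoided".
- **Section 6.3.1, second bullet:** "Co-administration with moderate CYP3A4 inhibitors (e.g., erythromycin, fluconazole) or PgP inhibitors should be used with caution". If a patient needs one, everolimus is to be reduced, by an amount that is not stated.
- **Section 6.3.1, inducer bullet:** strong CYP3A4 inducers are to be avoided. If one is required, raising everolimus in 5 mg steps to at most twice the current dose should be considered. The bullet names six drugs: phenytoin, carbamazepine, rifampin, rifabutin, phenobarbital and St. John's wort.
- **Section 6.3.1, table references:** "Please refer to Table 6-6 listing relevant inducers and inhibitors of CYP3A and Table 6-7 for a list" (of PgP substrates, inducers and inhibitors).
- **Table 6-8** lists fluconazole as a moderate CYP3A inhibitor. **Table 6-9** lists PgP inhibitors without any grade of strength, and has St. John's wort both among the inducers and among the inhibitors.
- **Table 6-1a** has three everolimus levels: 10, 5 and 2.5 mg daily. Section 6.2.1 allows at most two reductions.
- **Section 6.3.2**, headed "Prohibited concomitant therapy", says there is none.

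**The concern.** An investigator who follows the text as written can reach different actions for the same patient, depending on where the reading starts. For fluconazole and for PgP inhibitors the choice is between withholding the drug and giving it with less everolimus. For St. John's wort, if it is taken despite the advice against it, one rule points to more everolimus and another to less.

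The gap in the dose ladder is a separate problem that can be foreseen. Three of the six named strong inducers are anticonvulsants (phenytoin, carbamazepine, phenobarbital). The eligibility criteria do not exclude them, and seizure reduction is a secondary endpoint. A patient whose dose was raised for such a drug and who then has a toxicity meets reduction rules written for a ladder that does not contain the patient's dose.

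Everolimus is given in all three arms, so the matter is not confined to one of them. What is at stake is consistent and safe handling of everolimus dosing.

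**Working it through.** The plan states no figure on this point, so there is none to reproduce. The check sets the rules side by side, compares the drug lists, and works through the dose ladder.

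**1. Rules side by side**

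| Drug or class | One place | Another place |
|---|---|---|
| Fluconazole | 6.2.2.3: avoid in all patients; strong inhibition | 6.3.1 and Table 6-8: moderate inhibitor; caution, and reduce everolimus if required |
| PgP inhibitors | 6.3.1, first bullet: avoid | 6.3.1, second bullet: caution, and reduce everolimus if required |
| St. John's wort | 6.3.1, inducer bullet: avoid; if required, consider an increase to at most twice the dose | Table 6-9: also a PgP inhibitor, so avoid, or reduce everolimus |

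**2. Overlap of the lists.** Table 6-8 has 16 moderate CYP3A inhibitors and Table 6-9 has 31 PgP or dual inhibitors. Four drugs are in both: erythromycin, diltiazem, verapamil and dronedarone. All four fall under the first bullet (avoid) and the second (caution). Erythromycin is one of the second bullet's own two examples. Of the six named strong inducers, only St. John's wort is also in the PgP-inhibitor list, and none is in the CYP3A inhibitor lists.

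**3. Table references.** Table 6-6 is the pneumonitis table and Table 6-7 is the temozolomide adjustment table. The interaction lists are Tables 6-8 and 6-9. Two of two references are wrong.

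**4. Dose ladder.** From the 10 mg starting dose:

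- Ceiling for a strong inducer: 2 × 10 = 20 mg, reached through 10 + 5 = 15 mg and 15 + 5 = 20 mg.
- Top of Table 6-1a: 10 mg. Neither 15 nor 20 mg is a level.
- Tables 6-2 and 6-3 call for a one-level reduction after various toxicities. From 20 mg, that could be read as undoing one increment (20 − 5 = 15 mg), going to the top level (10 mg), or going to the first reduced level (5 mg). Nor is it stated whether a return to 10 mg counts toward the limit of two reductions. These readings only show the ambiguity.
- Exception: Section 6.2.2.6 and Table 6-6 describe the pneumonitis step as about half the previous dose, which gives 0.5 × 20 = 10 mg or 0.5 × 15 = 7.5 mg.

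**5. Spread for St. John's wort, as an illustration.** Starting from 10 mg, the inducer rule allows up to 20 mg. The inhibitor rule gives no size for the reduction. Assuming one or two levels of Table 6-1a, the result is 5 or 2.5 mg. The nominal doses then differ by 20 / 5 = 4-fold to 20 / 2.5 = 8-fold. This applies only if the herb is taken despite the advice to avoid it.

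**The case against.** The strongest reply is that most of these conflicts can be read away.

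- **Fluconazole.** Section 6.2.2.3 is advice on mouth ulcers, and 6.3.1 covers a patient who needs a moderate inhibitor. Together they could form a sequence: avoid, and if unavoidable, reduce. It is true that the dose direction is not reversed. But 6.2.2.3 makes no exception for need, applies to all patients, and gives strong inhibition as its reason, which 6.3.1 and Table 6-8 contradict.
- **PgP inhibitors.** The opening sentence of the interaction rules in 6.3.1 can be read as applying the word strong to PgP inhibitors too, so the bullets might mean avoiding strong ones and taking care with the rest. That may be the intent, but it cannot be carried out, because Table 6-9 has no grades.
- **St. John's wort.** The inducer rule names it and starts from avoidance, so a careful reader may put that rule first. This narrows the conflict but does not remove it, since Table 6-9 gives both classifications.
- **Table references.** The correct tables follow directly after the sentence and are correctly titled in the list of tables. The practical effect is small.
- **Prohibited therapy.** Section 6.3.1 itself bars other anticancer and investigational agents and requires withdrawal from the study before another anticancer agent is given. The entry in 6.3.2 is mainly misplaced labelling.
- **Safeguards.** Patients must consult the investigator before taking any medication, are asked at each visit, and have medications recorded. No participating sites are listed, so variation would lie between investigators or occasions rather than between sites. These safeguards bring the question to an investigator, who must still answer it from conflicting text.

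A reader might also infer that aprepitant has opposite instructions, since Table 6-8 lists it among the inducers ("amprenavir, aprepitant, armodafinil (R-modafinil), dexamethasone") and among the moderate inhibitors ("aprepitant, atazanavir, casopitant, cimetidine"). The documents do not support that. The dose-increase rule covers a closed list of strong inducers that omits aprepitant, so only the moderate-inhibitor rule gives it an action. Amprenavir, ritonavir and tipranavir are likewise only listed twice, and known HIV seropositivity is an exclusion. Being listed as both inducer and inhibitor is not in itself an error.

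**Conclusion.** The point holds as a matter of internal consistency. Fluconazole and the PgP inhibitors each have two actions that cannot both be followed, and four named drugs fall under both PgP bullets. One product, St. John's wort, has opposite dose directions, and only if it is given despite the advice to avoid it. Both table references are wrong. For a patient on a raised dose, the one-level reduction and the two-reduction limit are undefined except for the pneumonitis step. The entry in 6.3.2 is a minor labelling fault.

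A reader might infer that these faults shift the toxicity count in the accrual-suspension rule of Section 9.4, or distort the PFS estimates. The documents do not support that. They give no rate of use for these drugs, no exposure or toxicity figures for the combinations, and no link to discontinuation. The effect can be neither computed nor assumed. The 4- to 8-fold spread is in nominal dose, not exposure, and rests on an assumed size of reduction.

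The sponsor should act because the same patient can be handled in incompatible ways under the stated rules, which is a safety matter.

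**What to change.** Reconcile Table 6-1a, Section 6.2.2.3, Section 6.3.1, Tables 6-8 and 6-9, and Section 6.3.2:

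1. Give each drug or class one action. Either grade the PgP inhibitors in Table 6-9 or state one rule for all of them. Say which rule governs a drug that is listed in two classes, including St. John's wort.
2. Change the references in 6.3.1 to Tables 6-8 and 6-9.
3. State how Table 6-1a, the one-level reduction and the two-reduction limit apply to a patient whose everolimus was raised for an inducer.
4. Move the bars on other anticancer and investigational agents into 6.3.2 in place of the present entry.

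Which clinical rule applies in each case is for the sponsor to decide; nothing here favors one. The cost is one amendment, with the reviews in Sections 10.2 and 10.4, and a note to investigators. Sample size, visits and analyses do not change.

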**Table 6-1a      Everolimus dose levels**

Dose level	Dose and schedule
0 (starting dose)	10 mg daily
-1	5 mg daily
-2	2.5 mg daily

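### When a strong CYP3A4 inducer is stopped, Section 6.3.1 returns everolimus to the pre-inducer dose, with no exception for a toxicity reduction made while on the inducer

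*Combined protocol and SAP*

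**What the plan says.** The interaction bullets in Section 6.3.1 of the combined protocol and SAP are offered as advice ("the following are recommended"). Strong CYP3A4 inducers should be avoided. If one is required, an everolimus increase "up to twice the currently used daily dose should be considered", in 5 mg increments. The first increment comes 7 days after the inducer starts. The second is conditional: "If no safety concerns are seen within the next 7 days, the dose can be increased again". The ceiling is twice the earlier dose, so a patient on 10 mg may go to 15 mg and then 20 mg.

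The aim and its evidence base are stated together: "This dose adjustment of everolimus is intended to achieve similar AUC to the range observed without inducers", and then "However, there are no clinical data with this dose adjustment in patients receiving strong CYP3A4 inducers".

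The exit rule follows: "If the strong inducer is discontinued the everolimus dose should be returned to the dose used prior to initiation" of the inducer. It carries no condition.

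The moderate-inhibitor bullet in the same section does mention toxicity: "Additional dose reductions may be required to manage toxicities". Its own return rule, after a washout of 2 to 3 days, is also unconditional.

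Table 6-1a ("Everolimus dose levels") lists 10 mg, 5 mg and 2.5 mg daily, with nothing above 10 mg.

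**The concern.** The return rule is meant to undo an increase made to offset induction. As worded, it also undoes a decrease made for toxicity while the inducer was in use, and it does so just as drug clearance slows.

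What is at stake is the safety of the individual patient, and possibly that patient's access to the drug. Under Tables 6-2 and 6-3, a recurrent grade 4 toxicity after a reduction means stopping everolimus. Under Section 6.2.1, a patient already reduced by two levels who needs another reduction must also stop. In Arms 1 and 3, stopping everolimus ends all study treatment.

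The setting is plausible in this population. Three of the six strong inducers named in Section 6.3.1 are anticonvulsants (phenytoin, carbamazepine, phenobarbital). Seizure frequency is a secondary objective. Section 6.3.2 prohibits no concomitant therapy. The title of the phase I combination study in the reference list separates patients by use of enzyme-inducing anticonvulsants.

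**Working it through.** The plan gives no figure to reproduce. The check is a reading of the dosing text followed by simple ratios.

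**Is there an exception elsewhere?** Section 6.2.1 permits dose adjustment for intolerance but mentions neither inducers nor re-escalation. Tables 6-2, 6-3 and 6-6 hold, lower or stop everolimus; none steps a reduced dose back up or says what becomes of a reduction when an inducer is withdrawn. In the inducer bullets, the only safety condition governs the second upward increment. No written exception was found. A reduction made before the inducer started is preserved, because the return is to the dose in use at that time.

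**Inputs.** Pre-inducer dose 10 mg; lower levels 5 mg and 2.5 mg (Table 6-1a); possible doses on the inducer 15 mg and 20 mg (Section 6.3.1); return dose 10 mg. F is the exposure without the inducer divided by the exposure with it, at the same dose. The documents do not give F. I assume 1.5 to 2; the upper value is suggested by the permitted doubling and the stated AUC aim.

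**Cut from 10 to 5 mg on the inducer.** Milligram change on return: 10/5 = 2. The event occurred at 10 mg with the inducer; the patient now takes 10 mg without it. The dose is the same, so exposure relative to the event is F, which is at least 1 whatever the size of the induction. This comparison does not need dose-proportional exposure.

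**Cut from 5 to 2.5 mg on the inducer.** Milligram change: 10/2.5 = 4. Relative to the 5 mg event dose: 10/5 = 2.

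**Cut to 10 mg on the inducer.** Milligram change: 10/10 = 1. Exposure rises by F, again a same-dose comparison.

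**Illustrative sizes.** If exposure is also taken as proportional to dose, exposure after return is 10F/(reduced dose) relative to the reduced exposure, and 10F/(event dose) relative to the latest event. Ranges are for F = 1.5 to 2.

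| Event dose to reduced dose | Relative to reduced exposure | Relative to event exposure |
|---|---|---|
| 20 to 15 mg | 1.0 to 1.33 | 0.75 to 1.0 |
| 20 to 10 mg | 1.5 to 2.0 | 0.75 to 1.0 |
| 15 to 10 mg | 1.5 to 2.0 | 1.0 to 1.33 |
| 10 to 5 mg | 3.0 to 4.0 | 1.5 to 2.0 |
| 5 to 2.5 mg | 6.0 to 8.0 | 3.0 to 4.0 |

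The rows starting at 20 or 15 mg rest on interpretation, because Table 6-1a defines no step from those doses. The nearest textual support is the pneumonitis guidance (Section 6.2.2.6 and Table 6-6), which describes restarting at roughly half the previous dose; from 20 mg that is 10 mg. The rows starting at 10 and 5 mg use defined levels.

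**The case against.** The strongest answer is that the return sentence belongs to the inducer adjustment and tells the clinician to remove the inducer-driven increase. A patient already cut to 5 mg has no increase left to remove. Section 6.2 governs toxicity dosing and contains no step back up, which suggests that reductions persist. The bullets are recommendations, and Section 6.2.1 allows adjustment for intolerance. Much of this stands: a careful investigator may keep the lower dose without breaching the protocol. But none of it is written as an exception, and the one sentence that addresses this moment points the other way.

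A second objection is that a patient who started before the inducer has already taken 10 mg without it. At F = 2, the path from 20 to 10 mg returns to that same exposure. This is correct, but the reassurance is limited, because the patient has since had an event that required a reduction.

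A third is reach. A required inducer, a toxicity reduction and then inducer withdrawal must occur in that order, and nothing in the documents shows how often strong inducers are used in this trial. Laboratory tests every cycle and clinical assessments every 2 or 3 cycles could detect a problem. That also stands, though detection would come after the re-exposure.

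A reader might infer from the toxicity sentence in the inhibitor bullet that an exception was written there and left out for inducers. The text does not support this: the inhibitor return rule is equally unconditional.

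**Conclusion.** The gap is real and the point is worth considering. A stated rule, followed literally, raises exposure in a patient whose dose was recently lowered for toxicity. The firmest case is the 10-to-5 mg reduction: the dose doubles to that of the latest event, and exposure is at least that of the event for any F of 1 or more. For a patient cut to 10 mg, exposure rises by the unknown F. The multiples in the table also depend on the assumed F and, across different doses, on dose-proportional exposure.

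Three stronger readings go too far. One is that every path returns the patient to at least the event exposure: from 20 mg the ratio is 0.75 at F = 1.5, and after a 20-to-15 mg cut the rise above the reduced exposure is small or nil. Another is that the protocol compels re-escalation: the bullets only recommend. The third is that the trial's results are compromised: PFS-33 and PFS-38 are not affected, no effect on the Section 9.4 discontinuation counts is claimed, and the number of patients concerned is not given.

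**What to change.** Replace the return sentence in Section 6.3.1 with wording such as:

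> When a strong inducer is stopped, give everolimus at the pre-inducer dose or the current dose, whichever is lower. Do not raise a dose that was reduced for toxicity during inducer use. Where such a reduction was made and the dose on the inducer is 10 mg or less, the investigator may consider one further level down (Table 6-1a) as induction wears off. This step does not count as a toxicity reduction under Section 6.2.1.

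Under the same assumptions, a patient cut from 10 to 5 mg who stays at 5 mg has 5F/10 = 0.75 to 1.0 of the event exposure. If the optional step to 2.5 mg is taken, exposure is 2.5F/5 = 0.75 to 1.0 of the reduced exposure. Holding the dose alone does not offset lost induction, which is why the optional step is there. If F is above 2, exposure still rises: at F = 3 the optional step gives 2.5 × 3/5 = 1.5 times the reduced exposure, against 10 × 3/5 = 6 under the present text.

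Halving should not be mandatory. Rounded down to a Table 6-1a level, it would send 15 mg to 5 mg, where the present rule is nearly neutral, and it would fix a factor for which the protocol says there are no clinical data. Nor should a patient tolerating 2.5 mg be forced to stop.

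The cost is a short text change, with no new visits, data or analyses. The downside is that a few patients may remain on a lower dose than they could tolerate without the inducer. The same lower-of-the-two wording could be applied to the inhibitor return rule.
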